11.10 Trial day / Treatment day

Trial day is defined relative to the date of randomization. Treatment day is defined relative to the date of start of treatment (i.e. treatment day 1 is the day of the first dose of IMP). There will be a second start of treatment on the day of first administration of Evobrutinib during OLE labeled OLE Treatment day.

The day before the start date of treatment is defined as treatment day -1, i.e., there is no treatment day zero.

11.11 Repeated and unscheduled measurements

Repeated and unscheduled measurements are included in the listings. Data collected at both scheduled and unscheduled visits will be used for shift analyses.

By-visit summary statistics should be programmed based on assessments at both scheduled and unscheduled visits. Assessments at unscheduled visits will be included according to the visit windowing approach described below. A by-visit summary table/figure will include a footnote indicating whether assessments from unscheduled visits are included in the analysis.

For by-visit tabulations, in case of multiple assessments (including unscheduled) linked to the same visit, the first available assessment (in chronological order) will be included in the summary of a visit. This rule doesn't apply to baseline where the latest assessment before day 1 or OLE day 1 is taken.

Repeated and unscheduled measurements will be reported in the listings.

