examination prior to study start. The Assessing Neurologist is responsible for all EDSS assessments beginning at Screening and including all unscheduled visits initiated by a new or changing symptom potentially related to MS, as requested by the Treating Investigator. Throughout the trial, the Assessing Neurologist will be blinded to the participant's treatment, laboratory data, AE profile, any changes in safety assessments, and prior EDSS scores. The Assessing Neurologist must complete the EDSS prior to any treatment with steroids or other therapeutics intervention(s) that may alter the participant's neurological state, where possible. Both the Treating Investigator and the participant will be informed of the importance of not discussing these issues with the Assessing Neurologist to prevent unblinding.

PPD . A local radiologist will also review all MRI scans for safety and provide a report to the Treating Investigator, containing only nonMS pathology information.

The CRO will also provide a qualified neurologist who will adjudicate whether relapses meet the definition of a qualifying relapse (see Section 7.3.3) and review systematically the EDSS to determine if there is a lack of efficacy/disease progression. The scope of this review will be described in detail in the Medical Monitoring Plan.

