7.1.4 Unscheduled Visit for Neurological Worsening and Relapse **Assessment**

Participants should be instructed that if, at any point during the trial, they suspect that they are experiencing new or worsening neurological symptoms, including possible relapse, they should contact the Investigator as soon as possible after the onset of symptoms. If necessary, the participant should be evaluated by the Investigator within the clinic and every effort should be made to complete this evaluation within 1 week after the start of symptoms. Any assessments needed to confirm the relapse should be performed at the discretion of the Investigator. Details should be documented within the relevant section(s) of the eCRF. The definition of a qualifying and nonqualifying relapse is provided in Section 7.3.3.

If an MRI scan is indicated at an Unscheduled Visit for Neurological Worsening and Relapse Assessment, it should be performed prior to initiating corticosteroid therapy, where possible. In addition, care should be taken to avoid the participant being exposed to gadolinium more than once in a 4-week period, i.e., it may be necessary to cancel the MRI scan at the next scheduled visit (all other assessments should be completed at the visit as normal).

The following will be performed at an Unscheduled Visit for Neurological Worsening and Relapse Assessment:

- Review of concomitant medications and procedures, evaluation of AEs, disease activity assessment (relapse assessment, EDSS), complete physical examination, vital signs, and a neurologic exam;
- 12-lead ECG:
- Blood sample collection for safety assessments (hematology, chemistry);
- Urine collection for urinalysis, and, if necessary, microscopy and protein:creatinine ratio.

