11.13 Analysis visit windows

Assessments may be made at times other than the nominal times of planned visits, due to participant scheduling issues, unscheduled visits, or early treatment termination visits.

Analysis visit windows for efficacy and safety endpoints, will be used to incorporate unscheduled assessments in by-visit summaries. For participants discontinuing treatment during the OLE, the premature End of Treatment (EOT) assessment will be windowed appropriately, prior to the analysis, for safety.

For the calculation of analysis visit using the time windows, 1 month is expressed as 30 days.

As the schedule of assessments is different for each visit, specific time windows must be used for each endpoint. They are defined in Appendix 19.3.

For all biochemistry parameters, the same schedule of assessment is considered with all visits possible per protocol.

If there are multiple assessments within a same visit window, then the one closest to the target day will be used. If 2 assessments have the same difference with target day, the earlier one will be used.

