16.4 Expanded Disability Status Scale (EDSS)

Descriptive statistics for the EDSS score and EDSS CFB at each visit during the DBP and the OLE period combined will be provided by treatment group and overall on the mITT analysis set.

In addition, descriptive statistics for the EDSS score and EDSS CFB at each visit during the OLE period only will be provided by treatment group and overall on the mITT-OLE analysis set (early treatment discontinuers during OLE will be presented at 'EOT' visit).

Descriptive statistics for categorical EDSS CFB, i.e., number and proportion improving, stable, or worsening, will also be reported for each time point. Here improvement is defined as a decrease of 1.0 point or more, stable condition as a change of no more than half a point in either direction and worsening as an increase of 1.0 point or more.

Mean CFB in EDSS will be presented on mITT analysis set as a by-year line plot during DBP and OLE period combined. The plot will be provided for each treatment group and overall, with a vertical line segment at each visit representing \pm SE (jittered if needed for legibility), and with all treatment groups included in a single figure.

Additionally, the plot of mean CFB in EDSS will be presented for OLE period only (OLE Week 48 to OLE Week 336 and EOT) on mITT-OLE analysis set.

A listing will be provided for EDSS data, by participant and by timepoint for the DBP and OLE treatment period combined.

17 Safety Evaluation

The subsections in this section include specifications for summarizing safety endpoints that are common across clinical trials such as adverse events, laboratory tests and vital signs.

All outputs will be provided on the OLE period if not otherwise indicated.

Safety analyses will be based on the SAF for summaries on the DBP + OLE period and on the SAF-OLE for summaries on the OLE period, according to the as-treated principle.

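### SAP 11.11 and 11.13 conflict on which assessment represents an analysis visit, and the first-in-time rule would let a symptom-triggered EDSS replace a completed annual value

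*SAP*

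**What the plan says.** **Unscheduled values enter efficacy summaries.** SAP 11.11: "By-visit summary statistics should be programmed based on assessments at both scheduled and unscheduled visits". SAP 11.13 makes the scope explicit: "Analysis visit windows for efficacy and safety endpoints, will be used to incorporate unscheduled assessments in by-visit summaries". Neither 16.1 (MRI) nor 16.4 (EDSS) makes an exception.

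**There are two selection rules.** When several assessments belong to one visit, unscheduled ones included, SAP 11.11 says that "the first available assessment (in chronological order) will be included in the summary of a visit". SAP 11.13 says: "If there are multiple assessments within a same visit window, then the one closest to the target day will be used".

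**EDSS windows are wide.** In SAP Appendix 19.3, OLE Week 48 (target day 336) is [169, 504) and OLE Week 96 (target day 672) is [504, 840). Windows to Week 288 have the same form. Week 336 (target day 2352) is [2184, 2382). Protocol Tables 2 and 3 schedule OLE EDSS every 48 weeks, within ±7 days up to Week 192 and ±14 days after that.

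**Unscheduled EDSS is mostly symptom-triggered.** Protocol 7.1.4 asks participants to make contact if "they suspect that they are experiencing new or worsening neurological symptoms, including possible relapse". The procedures at that visit include "disease activity assessment (relapse assessment, EDSS), complete physical examination, vital signs, and a neurologic exam". The opening text of Protocol Section 7 makes the Assessing Neurologist responsible for EDSS, "including all unscheduled visits initiated by a new or changing symptom potentially related to MS", and wants it done before steroids where possible. One exception is in Protocol 7.1.6: an EDSS on resuming treatment after a gap of at least 4 weeks, whatever the symptoms.

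**Output.** SAP 16.4 reports by-visit mean EDSS change and a three-way category, with "worsening as an increase of 1.0 point or more". In the OLE-only summary, early discontinuers' values appear at EOT.

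**The concern.** Whether an extra EDSS exists depends largely on the outcome being summarised. A score taken during a suspected relapse, possibly months before the annual visit, could be tabulated as that year's disability value. If the participant then recovers, the table shows worsening that the completed annual examination did not find. EDSS change by OLE visit is a named OLE endpoint (Protocol 8.3.4, SAP 6), and its two summaries, mean change and proportion worsened, would both be pushed upward.

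The conflict between the two rules matters because it decides the size. Two programmers following the SAP faithfully could produce different annual EDSS tables from the same data.

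**Working it through.** **Can the two rules be reconciled?** One could read 11.11 as covering repeats at a single nominal visit and 11.13 as covering windows. But 11.11 names unscheduled assessments, and these attach to a visit only through the windows. Both rules therefore govern the same choice.

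**Window arithmetic (Appendix 19.3).** Week 48: 336 − 169 = 167 days before target, 504 − 336 = 168 after. Week 96: 672 − 504 = 168 before, 840 − 672 = 168 after. Week 336: 168 before, 2382 − 2352 = 30 after.

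**Assumptions, none from the documents.** Unscheduled EDSS occur as a Poisson process at r = 0.1, 0.2 or 0.3 per year. The score rises by 1.0 or 1.5 points at that visit, with full recovery by the scheduled visit. Background change has mean 0 and SD 0.5, rounded to half points. Scheduled visits are uniform within their allowed range, and 0, 10 or 20% are missing. The plan states no figure to reproduce. Results come from a simulation of the Week 96 window with 400,000 participants per scenario; the formulas below check it.

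**Step 1: share of completed annual values replaced.**
- Rule 11.11: any unscheduled EDSS in the 168 days before target wins, so the share is 1 − exp(−r × 168/365.25).
- Rule 11.13: the unscheduled EDSS must lie nearer to target than the scheduled visit. With ±7 days the mean distance is 3.5 days, so the share is about r × 7/365.25. With ±14 days it is about r × 14/365.25.

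| r per year | 11.11 | 11.13, ±7 days | 11.13, ±14 days |
|---|---|---|---|
| 0.1 | 4.5% | 0.2% | 0.4% |
| 0.2 | 8.8% | 0.4% | 0.8% |
| 0.3 | 12.9% | 0.6% | 1.1% |

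Formula and simulation agree.

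**Step 2: effect on the summaries, no scheduled visit missing.** Mean shift is the share replaced times the rise.
- Rule 11.11: 0.045 × 1.0 = 0.05 up to 0.129 × 1.5 = 0.19 points.
- Rule 11.13: at most 0.01 points.
- Worsened share with scheduled values only: P(Z ≥ 1.5) = 6.7%. With a rise of 1.0 point it becomes P(Z ≥ −0.5) = 69.1% among those replaced. At r = 0.2 under 11.11: 6.7% + 8.8% × (69.1% − 6.7%) = 12.2% (simulated 12.1%).
- Across scenarios: 9.5% to 17.8% under 11.11, and 6.8% to 7.2% under 11.13.

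**Step 3: scheduled visits missing.** Under 11.13, a participant without a scheduled EDSS takes any unscheduled value in the 336-day window, with probability 1 − exp(−r × 336/365.25). At r = 0.2 this is 16.8%. With 10% missing, the unscheduled share of reported values is (0.9 × 0.0038 + 0.1 × 0.168)/(0.9 + 0.1 × 0.168) = 2.2%, as simulated. Over 10 to 20% missing:
- Rule 11.13: 1.1% to 6.3% of values are unscheduled, mean shift is +0.01 to +0.09, and worsened is 7.4% to 12.0%.
- Rule 11.11 at 20% missing: worsened is 10.7% to 22.1%.

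**Step 4: leavers, not simulated.** If a participant has a relapse-time EDSS in a window and then stops treatment, the final EDSS is shown at EOT in the OLE-only summary. The relapse-time score can then be the only value left for that annual visit, under either rule.

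**The case against.** **11.13 may be the operative rule.** It is the dedicated windowing section, and 11.11 defers to it for slotting. If it governs, a completed annual visit is almost always used. This stands, and it is why the bias is conditional. But 11.11 states its own rule for by-visit tables, so the SAP does not secure the milder result.

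**The assumed rise is severe.** Protocol 7.3.3 lets a relapse qualify on examination changes alone, so EDSS need not rise. If only half of these visits show a rise of 1.0 point, at r = 0.2 under 11.11 the mean shift falls to 0.088 × 0.5 = 0.044, and worsened to 6.7% + 8.8% × 0.5 × (69.1% − 6.7%) = 9.4%. Incomplete recovery would also shrink the bias. The direction remains.

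**Baseline can work the other way.** SAP 11.6 allows an unscheduled value as OLE baseline. A relapse-time baseline would push change downward. This is correct, and it means that the net direction is not guaranteed for every participant.

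**A strict scheduled-only filter is also selective.** It drops relapsing participants who miss the annual visit. Protocol 7.1.4 and 7.3.1 also allow an unscheduled scan to cancel the next scheduled MRI. This stands, and the fix allows for it.

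**The consequence is limited.** SAP 16 has no hypothesis testing, a footnote discloses unscheduled data, EDSS is listed by participant, and relapses are reported separately. This limits the weight of the point, but a footnote does not correct an estimate, and no scheduled-only summary is specified.

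**Conclusion.** The point holds for EDSS, conditionally. The documents establish the conflict between the rules, the window widths, and the predominantly symptom-driven origin of unscheduled EDSS. Under 11.11 the upward bias could be material. Under 11.13 it is small unless the scheduled visit is missed or the participant leaves with the final EDSS shown only at EOT. The percentages are illustrative because every rate and effect size is assumed; only the direction of the replacement effect and the contrast between the rules follow from the plan.

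A reader might infer four stronger things that the documents do not support:
- *That the bias is serious whichever rule is used.* With the scheduled visit present, 11.13 removes nearly all of it.
- *That unscheduled EDSS exists only because a participant worsened.* The trigger is suspicion, and the post-gap EDSS has another cause.
- *That MRI summaries are similarly biased.* Unscheduled MRI is done only if indicated, SAP 16.1 has no worsened category, and no size was derived.
- *That arms with more relapses are affected more.* No figure supports this, and SAP 11.1 and 11.2 describe the same OLE dose sequence for all groups.

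The analyses are descriptive, so no type I error is affected. The ambiguity still warrants correction because it touches a named OLE endpoint.

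**What to change.** For the by-visit EDSS tables and plots in SAP 16.4, and for MRI in 16.1 for consistency:

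1. Delete the first-in-time rule from 11.11, so that one selection rule remains.
2. Use the scheduled assessment whenever one exists in the window.
3. Where only an unscheduled value exists, keep it out of the main by-visit row. Show it in a separate unscheduled/at-relapse row or a sensitivity summary, and report how many participants are affected, because this missingness is related to relapse.
4. For MRI, identify in the same way any unscheduled scan that replaced a cancelled scheduled one, so that it is not silently dropped.
5. Keep unscheduled values in the listings and in the safety shift tables.

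The cost is a short edit to 11.11 and 11.13, a visit-type filter in programming, one extra row or table, and a few more missing annual values in the main summary.

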- o. The Screening MRI scan should be acquired before randomization and dosing to allow for the readouts to be read by the central MRI reader (approximately 7 days).
- P. The IMP will be dispensed after randomization on Day 1 and at the indicated visits thereafter. All remaining IMP will be collected on Week 48.

u. To be completed before any other procedure takes place.

CC

w. All participants in the study, regardless of their liver function status, should have at least 1 test during the study period for ESR, hsCRP, and fibrinogen. This test may be conducted from a sample at any study visit.

Table 2 Schedule of Assessments – Optional OLE Period Week 0 to 96

Activity/ Assessment	OLE Day 1												(On T	Γrea	tmer	nt Vis	its: \	Veek	0 to	96										Unscheduled Visit
OLE Year										(OLE	Year	1												OL	E Yea	ır 2				
Visit number (for OLE)	1	1A	1.1	1B	2	2A	2.1	2B	3	ЗА	3.1	3B	4	4A	4.1	4B	4.2, 4.4	5	5.2, 5.4	6	6.2, 6.4	7	7.2, 7.4	8	8.2, 8.4	9	9.2, 9.4	10	10.2, 10.4	11ª	
Additional Visits for Tecfidera participants ONLY ^b	Х	Х		х	х	х		х	х	х		Х		х		Х															
Study Week	W 0	W 1	W 2	W 3	W 4	W 5	W 6	W 7	W 8	W 9	W 10	W 11	W 12	W 13	W 14		W16, W20	W 24	W28, W32	W 36	W40, W44	W 48	W52, W56	W 60	W64, W68	W 72	W76, W80	W 84	W88, W92	W 96°	
Study Day ± Visit Window	1 ±3	±3	±3	±3	28 ±7	±3	±3	±3	56 ±7	±3	±3	±3	84 ±7	±3	±3	±3	±3	168 ±7	±3	252 ±7	±3	336 ±7	±3	420 ±7	±3	504 ±7	±3	588 ±7	±3	672 ±7	
Obtain ICFd	Х																													Х	
Physical examination ^e	Х												Х					Х		Х		Х		Х		Х		Х			х
Vital signs ^f	Χ				Х				Х				Х					Х		Х		Х		Χ		Х		Χ		Х	Х
Neurological examination	X												Х					Х		Х		Х		Х		Х		Х		Х	х
Hematology ^f	Χ				Х				Х				Х					Χ		Х		Х		Χ		Х		Χ		Х	Х
Clinical chemistry ^f	Х				Х				Х				Х					Х		Х		Х		Х		Х		Х		Х	х
Supplemental Safety Visits including LFTs ^g	Х	Х	Х	Х	Х	х	Х	Х	Х	Х	Х	Х	Х	х	Х	Х	х	X	х	Х	х	Х	Х	Х	Х	Х	Х	Х	Х	Х	
CCI																															
Immunoglobulin levels ^f	Х																	Х				Х				Х				Х	
Urinalysis (microscopy, urine protein/ creatinine ratio) ⁱ	Х																	X						Х						X	х

Activity/ Assessment	OLE Day 1												•	On 1	Ггеа	tme	nt Vis	sits: \	Neek	0 to	96										Unscheduled Visit
OLE Year										(OLE	Year	1												OL	E Yea	ır 2				
Visit number (for OLE)	1	1A	1.1	1B	2	2A	2.1	2B	3	ЗА	3.1	3B	4	4A	4.1	4B	4.2, 4.4	5	5.2, 5.4	6	6.2, 6.4	7	7.2, 7.4	8	8.2, 8.4	9	9.2, 9.4	10	10.2, 10.4	11ª	
Additional Visits for Tecfidera participants ONLY ^b	х	х		х	х	х		х	х	х		х		х		Х															

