Study Week	W 0	W 1	W 2	W 3	W 4	W 5	W 6	W 7	W 8	W 9	W 10	W 11	W 12	W 13	W 14		W16, W20	W 24	W28, W32	W 36	W40, W44		W52, W56	W 60	W64, W68	W 72	W76, W80	W 84	W88, W92	W 96°	
Study Day ± Visit Window	1 ±3	±3	±3	±3	28 ±7	±3	±3	±3	56 ±7	±3	±3	±3	84 ±7	±3	±3	±3	±3	168 ±7	±3	252 ±7	±3	336 ±7	±3	420 ±7	±3	504 ±7	±3	588 ±7	±3	672 ±7	
CCI																														Х	
Urine pregnancy test (all countries) ^{k,l}	х				х				х				Х		х		Х	Х	Х	х	х	х	Х	Х	Х	Х	Х	Х	Х	Х	
12-lead ECG	Х																					Χ								Χ	Х
Chest X-ray	Χ																														
EDSS	Χ																					Х								Х	Х
Relapse assessment	Х	Х	X	Х	Х	Х	Х	Х	Х	Х	Х	Х	X	Х	Х	Х	Х	Х	Х	Х	Х	Х	Х	X	Х	X	Х	X	Х	Х	Х
MRI scan	Χ																					Х								Х	
Concomitant medications and procedures	Х	Х	X	Х	Х	х	X	х	Х	X	х	Х	X	Х	X	Х	Х	Х	Х	Х	Х	Х	Х	X	Х	X	Х	X	Х	X	х
AE evaluation	Χ	Χ	Χ	Χ	Х	Χ	Χ	Χ	Χ	Χ	Х	Χ	Χ	Χ	Χ	Χ	Х	Х	Х	Х	Х	Х	Х	Х	Х	X	Х	Х	Х	Χ	Х
Dispense IMP ^m	Х				Х				Х				Χ					Χ		Χ		Х		Χ		Χ		Χ		Х	
IMP compliance	Х				Х				Х				Χ					Χ		Χ		Х		Χ		Χ		Χ		Х	
CCI																															
C-SSRS (Since Last Visit Scale)	Х																					Х								Х	

CONFIDENTIAL INFORMATION

32/131

Global Version ID: 78691_4737384_6296959

AE=adverse event, ALT=alanine aminotransferase, AST=aspartate aminotransferase, CCI , CMV=cytomegalovirus, C-SSRS=Columbia-Suicide Severity Rating Scale, EA=early antigen, EBNA=Epstein-Barr nuclear antigen, ECG=electrocardiogram, eCRF=electronic case report form, EDSS=expanded disability status scale, ESR=erythrocyte sedimentation rate, GGT=γ-glutamyl-transferase, HAV=hepatitis A virus, HBc=hepatitis B core antigen, HEV=hepatitis E virus, CCI , hsCRP=high sensitivity C-reactive protein, ICF=informed consent form, Ig=immunoglobulin, IMP=investigational medicinal product, INR=international normalized ratio, LFT=liver function test, MRI=magnetic resonance imaging, MS=multiple sclerosis, VCA=viral capsid antigen.

- a. As described in Section 7.1.6, there may be a dosing delay between Visit 11 (Week 96) and Visit 12 (Week 108). In this circumstance, the participant should return to the study site when dosing resumes, and the procedures described in Section 7.1.6 should be performed.
- b. Visits 2 (Week 4) and 3 (Week 8) are applicable only for participants who received Tecfidera, and for participants who received M2951/placebo these visits are only for LFTs (Section 7.1.6 and Section 7.1.3).

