11.12 Early treatment termination assessments

By-visit summary statistics should be programmed based on assessments slotted according to the visit windowing approach described below. A by-visit summary table/figure will include a footnote indicating whether assessments from early treatment termination visits are included in the analysis based on slotting the assessment into the appropriate analysis visit window. The summary for the Early Treatment Termination visit (for assessments not slotted according to a visit window approach) will be distinguished from the OLE Week 384 visit, and the Early Study Termination visit from the summary for the OLE Week 388 visit.

For analyses by time period, data from Safety Follow-up will be included in the period in which the participant has discontinued. Data from Safety Follow-up will also be included in shift table to derive worst grade or value.

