16.1 MRI

Descriptive statistics for the number of T1 Gd+ lesions, new/enlarging T2 lesions and T2 volume at each visit (early treatment discontinuers during OLE will be presented at 'EOT' visit) during the OLE will be provided by treatment group and overall on the mITT-OLE analysis set.

Mean number of T1 Gd+ lesions and new/enlarging T2 lesions will be presented as a by-visit line plot for each treatment group during the OLE on the mITT-OLE analysis set, with a vertical line segment at each visit representing ± standard error (SE) (jittered if needed for legibility), and with all treatment groups included in a single figure.

A listing will be provided for the MRI assessment data, by participant and by timepoint for the OLE treatment period.

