17.7 Pregnancy Test

Results of pregnancy test (urine or serum) will be listed for OLE period based on SAF-OLE.

Analyses will be performed for the DBP+OLE period based on the SAF analysis set and for OLE period based on the SAF-OLE.

Data on immunoglobulin (Ig) levels, and CCl (see list of parameters in Appendix 19.2) will be summarized for the OLE period for observed values, change from OLE baseline values, and percent change from OLE baseline by treatment group and overall using descriptive statistics.

In addition, number and percent of subjects falling above, below, and within normal range will be summarized where applicable. Assessments made at the End of Treatment visit for treatment discontinuers will be windowed appropriately. Assessments made at the End of Trial visit for study discontinuers will be summarized separately from assessments made at Safety follow-up visit at OLE Week 388 End of Trial visit for study completers.

Additionally, descriptive statistics of absolute values of CCI will be provided for subjects falling above, below, and within normal range of the specific laboratory parameter. Summaries will be provided on OLE period for observed values, change from OLE baseline values, and percent change from OLE baseline by treatment group and overall.

Shift tables from OLE baseline value (low, normal, high) to end of OLE Period will be presented by treatment group and overall, for each Ig class and subclass, and parameters where applicable (see list of parameters in Appendix 19.2), using SAF-OLE analysis set.

[figure not shown]
Boxplots for each Ig class and subclass, (g/L), and CC (see list of parameters in Appendix 19.2) by treatment group and time point will be provided, for OLE period.

Line plots of median percent change from baseline will be provided by time point and treatment group on DBP and OLE combined periods for each Ig class and subclass, and (see list of parameters in Appendix 19.2).

(see list of parameters in Appendix 19.2) and Ig class and subclass levels will be listed by treatment group, participant and time point (where applicable). IgG values < 3 g/L (severe hypogammaglobulinemia) and IgG values < 6 g/L (hypogammaglobulinemia) will be flagged in the listing.

EAIR of infections

For definition of severe infections AESI, see Section 17.2.3 and Appendix 19.5.

Confidence interval of incidence rate will be calculated using the Garwood method for Poisson mean.

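### SAP 11.11 and 11.13 give conflicting rules for choosing one value per visit, and Appendix 3 has no OLE Week 12 hematology window for participants who came from evobrutinib or placebo

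*SAP*

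**What the plan says.** **Selection rule.** SAP 11.11 brings unscheduled records into by-visit summaries through the analysis windows: "Assessments at unscheduled visits will be included according to the visit windowing approach described below". When several records link to one visit, "the first available assessment (in chronological order) will be included in the summary of a visit". The only stated exception is baseline. SAP 11.13 covers the same situation differently: "If there are multiple assessments within a same visit window, then the one closest to the target day will be used". It uses the earlier record only when two are equally distant from the target.

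Some by-visit summaries have no window or target day. SAP 11.12 mentions an Early Treatment Termination summary "for assessments not slotted according to a visit window approach". SAP 16.1 (and likewise 16.4) says that "early treatment discontinuers during OLE will be presented at" the EOT visit. For immunoglobulins, section 17 says "Assessments made at the End of Trial visit for study discontinuers will be summarized separately".

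**Windows.** Protocol Table 2 marks hematology at OLE Weeks 4, 8, 12 and 24 and at later visits. Its row headed "Additional Visits for Tecfidera participants ONLY" does not mark Week 12. Footnote b says "Visits 2 (Week 4) and 3 (Week 8) are applicable only for participants who received Tecfidera", with LFTs only for everyone else at those visits. In the OLE hematology table of SAP Appendix 3, the evobrutinib/placebo column is empty for Weeks 4 to 16, and its Week 24 window is [2, 210). The Tecfidera column has [77, 98) for Week 12 and [140, 210] for Week 24.

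**The concern.** The two selection rules act on the same windowed data and can return different values. A programmer following 11.11 and one following 11.13 would produce different tables, and both could claim to have followed the plan.

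The hematology window is wrong under either rule. For participants from the evobrutinib and placebo arms, Week 12 is the first scheduled hematology after OLE Day 1, yet it has no column of its own.

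At stake are the OLE Week 24 hematology summary (observed value and change from OLE baseline) and the by-visit EDSS tabulations, including the improving/stable/worsening proportions. EDSS is sensitive because Protocol 7.1.4 triggers unscheduled visits on suspected worsening, whether or not a relapse is confirmed, and performs an EDSS there. Under 11.11, an unscheduled score earlier in the window replaces the annual one. Under 11.13 it does so only if it is nearer the target day.

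**Working it through.** **1. Inputs.** Table 2 visit windows: Week 12 is day 84 ± 7 (77 to 91) and Week 24 is day 168 ± 7 (161 to 175). Appendix 3, evobrutinib/placebo hematology: Week 24 window [2, 210), target day 168.

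**2. Both rules applied to hematology.** There are 15 × 15 = 225 combinations of on-schedule Week 12 and Week 24 days. Both samples fall in [2, 210) in all 225.

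| Rule | Sample reported as OLE Week 24 | Distance from day 168 |
|---|---|---|
| 11.11, first in time | Week 12 sample, days 77 to 91 | 168 − 91 = 77 to 168 − 77 = 91 days |
| 11.13, closest to target | Week 24 sample, days 161 to 175 | 0 to 7 days |

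The rules disagree in 225 of 225. An earlier unscheduled sample, say on day 30, would displace even the Week 12 sample under 11.11. Under 11.13 any later sample before day 210 beats the Week 12 sample, because the last day in the window, 209, is only 209 − 168 = 41 days from target. If there is no later sample, 11.13 also labels the Week 12 sample as Week 24.

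**3. Is the missing row deliberate?** The same participants have a Week 12 window for vital signs, [2, 126), and for biochemistry, [77, 91). A Week 24 window that opens on day 2 leaves no room for Week 12, so this is not a cell lost in text extraction. SAP section 15 agrees that Week 12 is a real visit for them: 12 kits × 8 days = 96 days of supply on OLE Day 1, with the next supply at Week 12 (former Tecfidera participants received 5 × 8 = 40 days).

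**4. How widespread is it?** I placed the scheduled OLE assessments at nominal days into every Appendix 3 OLE table with a visible schedule, for evobrutinib/placebo participants and excluding Week 0 rows. Row counts: hematology 21, vital signs 22, biochemistry 42, urinalysis 17, Ig 14, ECG 7, EDSS 7, MRI 7; total 137. Exactly one row, hematology Week 24, holds two scheduled assessments.

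**5. The rule conflict without the window error.** In the biochemistry OLE Week 36 window [238, 266), target 252, samples on days 240 and 252 give day 240 under 11.11 and day 252 under 11.13.

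**6. EDSS, illustration only.** The OLE Week 48 window is [169, 504) and its target is day 336, which leaves 336 − 169 = 167 days before target. The documents give no rate of unscheduled EDSS, so the rate r per participant-year is an assumption. P(at least one) = 1 − exp(−r × 167/365.25):

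| r | P |
|---|---|
| 0.04 | 1.8% |
| 0.10 | 4.5% |
| 0.20 | 8.7% |
| 0.40 | 16.7% |

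Given an annual EDSS at the target day, these are the participants for whom 11.11 would report an unscheduled score instead.

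**7. After the repair.** With Week 12 [2, 126) and Week 24 [126, 210), where 126 = (84 + 168)/2, each of the 225 pairs puts one sample in each window and the rules agree. They still diverge once an unscheduled sample appears: days 140 and 168 give 140 under 11.11 and 168 under 11.13. Both changes are therefore needed.

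**The case against.** The best defence is that 11.13 is the specific rule. It names the window and the target day and adds a tie-break, and all of that would be idle if first-in-time governed windowed data. On this reading 11.11 covers only repeats at one visit, and an on-schedule Week 24 sample is always chosen. The reading is sensible, but the SAP does not state it. The 11.11 rule expressly includes unscheduled records, which reach a visit only through the windows. The reading also does not restore the missing Week 12 column.

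The EDSS percentages rest on assumed rates and presuppose an annual EDSS in the same window. They are neither an upper bound nor a bias estimate, and the conclusion does not depend on them.

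It can also be said that EOT and End of Trial are normally single visits, so keeping 11.11 for them guards against a rare case. That is fair, but keeping it costs nothing, and 11.11 is the only visible rule for them.

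Finally, splitting one row does not reconcile the whole table. It has former Tecfidera rows for Weeks 6, 10 and 16 that the Table 2 hematology row does not mark, and [140, 210] overlaps the Week 36 window [210, 294) at day 210. These are further defects in the same table and do not weaken the point.

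**Conclusion.** The concern holds on both parts. The SAP contains two selection rules with no stated precedence, and one hematology window omits a scheduled visit for four of the five treatment groups.

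Under 11.11, an on-schedule participant's Week 24 hematology value is taken at least 77 days before target (84 at the nominal visit), and the column and its Total mix about 12 with about 24 weeks of OLE treatment. Under either rule, the Week 12 Total contains former Tecfidera participants only. Table 4 lists nine hematology parameters for boxplots. The missing window affects those plots too, although the SAP does not say whether the 11.11 rule, worded for tabulations, selects their data.

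The reach is modest. The window error touches one of 21 post-baseline OLE hematology columns for these groups. The final analysis has no hypothesis tests. Shift tables and listings keep all data, and ARR, time to relapse and AE rates do not use the rule. The hematology result assumes visits within the protocol's ± 7 days. The correction should be made because the plan, followed as written, mislabels or omits scheduled data.

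**What to change.** 1. In the Appendix 3 OLE hematology table, split the evobrutinib/placebo Week 24 row into OLE Week 12 [2, 126) and OLE Week 24 [126, 210), matching the vital-signs table for the same participants.
2. State that the closest-to-target rule of 11.13 governs wherever an analysis window exists. Limit the first-available rule of 11.11 to by-visit summaries without a window, such as Early Treatment Termination/EOT and End of Trial. Keep the baseline exception.

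While the table is open, check the former Tecfidera rows for Weeks 6, 10 and 16 and the shared day 210 against Table 2.

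The cost is one scope sentence and one row split in two. No new data are needed.
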